### **4.6.3 Analysis of Secondary Efficacy Endpoints**

#### *4.6.3.1 Objective Response Rate*

The ORR is defined as the proportion of patients with a best response of CR or PR. The primary analysis of ORR will be assessed by central radiology per mRECIST 1.1 for the ITT population.

The ORR and its two-sided 95% CI will be estimated using the exact binomial distribution (Clopper-Pearson).

Additionally, the best overall response following the hierarchical order of CR, PR, SD, PD, and not evaluable (NE) will be tabulated. Non-CR/Non-PD will be treated as SD.

A Cochran-Mantel-Haenszel (CMH) test will be performed to test for treatment difference. Stratification will be by the randomization stratification factors. An unstratified CMH test will be performed as a sensitivity analysis.

The following additional sensitivity analyses will be conducted to assess the robustness of the primary analysis:

- ORR assessed by central radiology per mRECIST 1.1 in the PP and RE Populations.
- ORR assessed by central radiology per mRECIST 1.1 in the ITT Population by each stratification factor.
- ORR as assessed by the Investigator in the ITT Population will be summarized for best overall response.

#### *4.6.3.2 Overall Survival*

Overall survival is defined as the time from randomization to the date of death. Patients who die before or on the data cutoff date will be considered to have had an OS event. All patients who do not have a death record prior to or on the cutoff date will be censored at the last date known alive.

The primary treatment comparison will be based on a stratified log-rank test using the ITT Population. The HR and its 95% CI will be estimated using a stratified Cox model with treatment as the explanatory variable and strata as the stratification factors. An unstratified log-rank test will be performed as a sensitivity analysis.

A rank preserving structural failure time (RPSFT) model will be applied as a supportive analysis to account for treatment crossover effects from regorafenib to avapritinib. The survival time gained/lost by receiving avapritinib after crossover in the regorafenib group will be estimated. The RPSFT reconstructs the survival duration of crossover patients as if they had never received avapritinib, assuming treatment acts by multiplying survival time by a given factor once a patient starts receiving avapritinib (Korhonen et al, 2012). See Appendix 2 (Section 7.4) for further details of implementing this method.

## **Avapritinib Statistical Analysis Plan Study BLU-285-1303**

Kaplan-Meier plots will be presented for overall survival for both the primary and sensitivity analyses.

### *4.6.3.3 Duration of Response*

Duration of response is defined as the time from first documented response (CR/PR) to earlier of the date of first documented disease progression or death due to any cause.

Patients without CR or PR will be excluded from this analysis. Patients who are still in response at time of data cutoff will be censored at their last valid assessment. Complete censoring rules (both European Medicines Agency [EMA] and United States [US] Food and Drug Administration [FDA]) are specified in [Table 2](#). The analysis will be primarily based on FDA Guidance for Cancer Trial Endpoints ([FDA, 2007](#)). The censoring rules based on the EMA Guideline on the evaluation of anticancer medicinal products in man will be used as a sensitivity analysis ([EMA, 2017](#)).

Duration of response will be analyzed for the responders (CR/PR) in the ITT Population using KM methods and will include the estimated median with two-sided 95% CI and the 25th and 75th percentiles. DOR at specific time-points (e.g., 3-, 6-, and 12-month, etc.) will be computed with respective standard errors using Greenwood's formula ([Klein, 2003](#)).

Sensitivity analyses will be conducted for DOR based on Investigator assessment per mRECIST 1.1. Both FDA and EMA censoring rules will be applied.

### *4.6.3.4 Disease Control Rate*

Disease control rate (DCR) is defined as the proportion of patients with a CR/PR of any duration, or SD lasting for 16 weeks from date of randomization. The response will be assessed per mRECIST 1.1. DCR and its two-sided 95% CI will be estimated for the ITT Population using the exact binomial distribution (Clopper-Pearson).

### *4.6.3.5 Response Rate by Choi Criteria*

The ORR per Choi response criteria ([Weng, 2013](#)) and its two-sided 95% CI will be estimated for the ITT Population using the exact binomial distribution (Clopper-Pearson).

The best overall response per Choi criteria following the hierarchical order of CR, PR, SD, PD, and NE will be tabulated.

### *4.6.3.6 EORTC-QLQ-C30*

All questionnaire analyses will be based on the ITT population, and only includes those patients with baseline assessments for each instrument.

The EORTC QLQ-C30 (version 3.0) is a 30-item questionnaire used to evaluate QoL, and includes five functional domains (physical (PF), cognitive (CF), role (RF), emotional (EF), and social (SF)), three symptom scales (fatigue (FA), nausea and vomiting (NV), and pain (PA)), a global health status / QoL scale (QL), and six single items (dyspnea (DY), insomnia (SL), appetite loss (AP), constipation (CO), diarrhea (DI), and financial difficulties (FI)).

**Avapritinib  
Statistical Analysis Plan Study BLU-285-1303**

All of the scales and single-item measures range in score from 0 to 100. A high score for a functional scale represents a high/healthy level of functioning, a high score for the global health status represents a high QoL, but a high score for a symptom scale / item represents a high level of symptomatology / problems. The scoring method is outlined in [Table 3](#).

**Table 3: Scoring the QLQ-C30 version 3.0**

	Scale	Number	Item	Version	Function
Global health Status /QoL	QL	2	6	29, 30	
Functional Scales					
Physical functioning	PF	5	3	1 to 5	F
Role functioning	RF	2	3	6,7	F
Emotional functioning	EF	4	3	21 to 24	F
Cognitive functioning	CF	2	3	20, 25	F
Social function	SF	2	3	26, 27	F
Symptom scales/items					
Fatigue	FA	3	3	10, 12, 18	
Nausea and vomiting	NV	2	3	14,15	
Pain	PA	2	3	9, 19	
Dyspnea	DY	1	3	8	
Insomnia	SL	1	3	11	
Appetite loss	AP	1	3	13	
Constipation	CO	1	3	16	
Diarrhea	DI	1	3	17	
Financial difficulties	FI	1	3	28	

\*Item range is the difference between the possible maximum and the minimum response to individual items.

Raw score (RS) is calculated as the average of item score when at least half of the items are not missing. A linear transformation to 0-100 will then be applied to get the score (S) use ranges provided in [Table 3](#).

For functional scales  $S = (1 - (RS - 1) / \text{range}) \times 100$

For symptom scales / items and global health status  $S = ((RS - 1) / \text{range}) \times 100$

Calculated scale scores will be descriptively summarized at baseline and Day 1 of each assessed cycle. Change and percentage change from baseline will also be summarized for post-baseline assessments.

Box plots of the change from baseline will be presented.

As a sensitivity analysis, cumulative density function (CDF) plots of QoL will be produced at Day 1 of each assessed cycle: the horizontal axis displays the absolute score change from baseline, and the vertical axis shows the proportion of patients whose absolute score change from baseline is less than or equal to the value indicated on the x-axis. Similar CDF plots will be produced for all 6 functional scales at Day 1 of each assessed cycle.

**Avapritinib**  
**Statistical Analysis Plan Study BLU-285-1303**

[figure not shown]
For physical functioning, pain, role functioning and appetite loss, the mean change from baseline to Week 12 will be compared between treatment groups using a t-test.

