Patients randomized to Arm B will receive regorafenib 160 mg PO QD for 3 weeks out of every 4 weeks (28 days) cycle (ie, 3 weeks on/1 week off). Patients who experience disease progression on regorafenib (Arm B), as confirmed by central radiology review, may be offered the opportunity to cross over to the avapritinib treatment arm (Arm A) after an evaluation of their disease progression and a washout period of 7 to 28 days after their last dose of regorafenib. Patients randomized to Arm B must consent to cross over to avapritinib treatment after disease progression.

At least 70% of the patients enrolled should be receiving the study drug as their third distinct TKI treatment for GIST, ie, no more than 30% of patients should be receiving the study drug as their fourth distinct TKI treatment for GIST. In addition, patients will receive best supportive care, excluding any additional anticancer therapy such as any systemic antineoplastic therapy (including kinase inhibitors and chemotherapy), radiation therapy, or surgery.

All patients will present to the study center on C1D1 for the first dose of study drug, vital sign measurements, safety monitoring, quality-of-life (QoL) assessment, PRO assessments, electrocardiogram (ECG) assessment, and AE recording. On Cycle 2 Day 1 (C2D1) and Cycle 3 Day 1 (C3D1), patients will present to study centers for physical examination, laboratory assessments, QoL assessments, PRO assessments, and AE/concomitant medication recording. For all subsequent cycles, all patients will attend study center visits every other cycle on Day 1 of odd cycles (ie, C5D1, C7D1 etc.) for safety monitoring including ECG, hematology, blood chemistry, QoL assessments, PRO assessments, and AE recording. At any point in time between treatment cycles patients should attend or contact the study center for AE reporting, evaluation, and medical intervention.

Tumor assessments will be performed at Baseline and then every 8 weeks ( $\pm 1$  week) counting from C1D1, regardless of the scheduled treatment cycles, ie, if study treatment is interrupted or discontinued for any reason, tumor imaging should continue according to an 8-week schedule until tumor progression is confirmed by central radiology review. Computed tomography with intravenous contrast is the preferred imaging modality, unless a site of disease is better evaluated by MRI.

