At least 70% of the patients enrolled should be receiving the study drug as their third distinct TKI treatment for GIST, ie, no more than 30% of patients should be receiving the study drug as their fourth distinct TKI treatment for GIST. In addition, patients will

receive BSC, excluding any additional anticancer therapy such as any systemic antineoplastic therapy (including kinase inhibitors and chemotherapy), radiation therapy, or surgery.

All patients will present to the study center on C1D1 for the first dose of study drug, vital sign measurements, physical exam, quality-of-life (QoL) assessment, PRO assessments, laboratory assessments, ECG and AE recording. In Cycle 2 Day 1 (C2D1), Cycle 3 Day 1 (C3D1), Cycle 4 Day 1 (C4D1) and Cycle 5 Day 1 (C5D1), patients will present to study centers for physical examination, vital signs measurements, laboratory assessments, QoL assessments, PRO assessments, ECG, and AE/concomitant medication recording. On C1D15 and C2D15, all patients will attend study center visits for vital sign measurements, serum chemistry measurements, and AE reporting. For all subsequent cycles, all patients will attend study center visits every other cycle on Day 1 of odd cycles (ie, C7D1, C9D1 etc.) for physical examination, vital sign measurements, laboratory assessments, QoL assessments, PRO assessments, ECG and AE recording. At any point in time between treatment cycles patients should attend or contact the study center for AE reporting, evaluation, and medical intervention.

[figure not shown]
Tumor assessments will be performed at Baseline and then every 8 weeks ( $\pm$  1 week) counting from C1D1, regardless of the scheduled treatment cycles, ie, if study treatment is interrupted or discontinued for any reason, tumor imaging should continue according to an 8-week schedule until tumor progression is confirmed by central radiology review. Computed tomography with intravenous (IV) contrast is the preferred imaging modality, unless a site of disease is better evaluated by MRI.

It is anticipated that patients will receive at least 1 cycle of avapritinib if randomized to Arm A and regorafenib if randomized to Arm B; no maximum treatment duration has been set. After C1, patients may continue to receive study drug until precluded by toxicity, noncompliance, pregnancy, withdrawal of consent, physician decision, PD, death, or closure of the study by the Sponsor.

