#### 10.5.3.2.3 Analyses of Health-Related Quality-of-Life

The EORTC-QLQ-C30 questionnaire will be used to collect data on the patient's functioning, disease-related symptoms, and health-related QoL. For all individual scores, eg, physical functioning, pain, role functioning, and appetite loss, etc, mean changes from baseline to Week 12 will be compared between treatment groups by a t-test. Post hoc analyses to explore thresholds for meaningful change using cumulative distribution function to determine clinical benefit will be outlined in the SAP.

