## **Avapritinib**

### **Statistical Analysis Plan Study BLU-285-1303**

- All individual EORTC-QLQ-C30 scores, including symptom and function scales, and the global health status score.
- ORR as assessed by Investigator per mRECIST 1.1.
- ORR as assessed by central radiology per Choi criteria.
- DCR is defined as the rate of CR or PR of any duration or stable disease (SD) lasting at least 16 weeks from the date of randomization.
- Duration of response defined as the time from first documentation of tumor response to disease progression or death due to any cause.
- Adverse events, serious AEs (SAEs), and changes in safety laboratory parameters, 12-lead ECG evaluations, and ECOG PS. The intensity of AEs will be assessed by the NCI CTCAE, version 4.03 or 5.0.
- Abdominal pain as measured by a numeric rating scale (0-10).

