**6. CHANGES TO PLANNED ANALYSES FROM THE PROTOCOL**

There is no change to planned analyses from the protocol.

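### The Week 12 QLQ-C30 comparison leaves the baseline score unused, and the SAP cuts the tested scores from all 15 to four without declaring it

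*SAP*

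**What the plan says.** **Method.** Protocol 10.5.3.2.3 plans a t-test on mean change from baseline to Week 12. SAP 4.6.3.6 keeps it: "the mean change from baseline to Week 12 will be compared between treatment groups using a t-test". Neither document names a covariate or a stratified version of this test.

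**Which scores.** The protocol's scope is broad: "For all individual scores, eg, physical functioning, pain, role functioning, and appetite loss, etc, mean changes from baseline to Week 12 will be compared". The four named scores are examples. The SAP applies the t-test to those four only. The rest are handled by summaries and plots: "Calculated scale scores will be descriptively summarized at baseline and Day 1 of each assessed cycle". SAP 1.4.2 still lists as a secondary endpoint "All individual EORTC-QLQ-C30 scores, including symptom and function scales, and the global health status score". SAP Section 6 then says: "There is no change to planned analyses from the protocol".

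**Which patients.** SAP 4.6.3.6 states: "All questionnaire analyses will be based on the ITT population, and only includes those patients with baseline assessments for each instrument". A change to Week 12 also needs a Week 12 form. The QLQ-C30 scoring rule deals with missing items, and the imputation rules in SAP 7.1 deal with dates. The visible text has no rule for a missing form.

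**Multiplicity.** SAP 4.6.1 limits the gate-keeping to PFS, ORR and OS.

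**The concern.** There are two separate points.

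First, a t-test on change scores fixes the weight on baseline at one, whatever the data show. A regression on baseline estimates that weight. The baseline form is already required for entry to the analysis and the stratification factors are known for every patient, so leaving them out gives a wider confidence interval than the collected data support.

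Second, the two documents disagree on which scores are formally compared, and the section meant to record departures says that there are none. In an open-label trial, an unexplained narrowing of the tested patient-reported scores invites a question about selective testing, even where there is an innocent reason.

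At stake are the precision of an additional secondary endpoint and the traceability of its analysis.

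**Working it through.** **Plan figure.** The documents give no SD, effect size, correlation or power for QLQ-C30, so there is no figure to reproduce. What follows is a comparison of methods.

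**Step 1: baseline adjustment.** Let r be the baseline to Week 12 correlation and k the Week 12 SD divided by the baseline SD. Both are assumptions (r from 0.3 to 0.7; k of 0.8, 1 and 1.25). In units of the baseline variance, and with the same patients in both analyses:

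- change score, per patient: 1 + k² − 2rk
- residual after regression on baseline, per patient: k²(1 − r²)
- variance ratio, ANCOVA to t-test: k²(1 − r²) / (1 + k² − 2rk); at k = 1 this is (1 + r)/2

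| k | r = 0.3 | r = 0.5 | r = 0.7 |
|---|---|---|---|
| 0.8 | 0.50 | 0.57 | 0.63 |
| 1 | 0.65 | 0.75 | 0.85 |
| 1.25 | 0.78 | 0.89 | 0.98 |

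Example (k = 1, r = 0.5): 0.75 / 1 = 0.75. At k = 1 the standard error falls by 19% at r = 0.3 (√0.65 = 0.806) and by 8% at r = 0.7 (√0.85 = 0.922).

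The denominator minus the numerator is 1 − 2rk + r²k² = (1 − rk)², which is never negative. In large samples the adjusted analysis therefore cannot have the larger variance. A simulation with 178 and 157 patients (40,000 runs, k = 1) gave 0.65, 0.75 and 0.86, in line with the formula. Any gain from the stratification factors would be extra and is not quantified.

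**Step 2: what a repeated-measures model adds.** This needs an assumed rate of lost Week 12 forms. As a rough proxy, take the proportion progression-free at the Day 57 scan under the sample-size assumptions (exponential PFS, control median 5 months, HR 0.67). Time is 56/30.4375 = 1.84 months:

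- regorafenib: 2^(−1.84/5) = 0.775
- avapritinib: 0.775^0.67 = 0.843

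Let C = 1/0.775 + 1/0.843 = 2.477, v0 = 1 − r², and v = the residual variance of the Week 12 score given baseline, C2D1 and C3D1. With equal SDs, and non-selective loss of the Week 12 form only, the variance ratio of MMRM to t-test is [2(v0 − v) + vC] / [2(1 − r)C]:

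| Correlation pattern | r = 0.3 | r = 0.5 | r = 0.7 |
|---|---|---|---|
| Equal at all visits | 0.639 | 0.726 | 0.811 |
| Decaying with time | 0.601 | 0.677 | 0.754 |
| ANCOVA, for reference | 0.65 | 0.75 | 0.85 |

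The further gain over ANCOVA is about 1 to 4 points of variance with equal correlations and 5 to 10 with decaying ones. Most of the gain comes from the baseline score.

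**Step 3: number of scores.** SAP 4.6.3.6 lists five functional domains, three symptom scales, one global scale and six single items: 5 + 3 + 1 + 6 = 15. The SAP tests 4, so 15 − 4 = 11 lose their planned comparison.

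**Step 4: false positives without multiplicity control.** At 0.05 each, and if the tests were independent, the chance of at least one is 1 − 0.95^4 = 0.19 for four scores and 1 − 0.95^15 = 0.54 for fifteen.

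**The case against.** **The t-test is the protocol's own method, it is valid, and the endpoint is not gated.** All true. The SAP did not introduce the t-test, and replacing it is itself a departure that must be declared. None of this answers the lost precision, and it does not touch the mismatch in scores.

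**The size of the gain is assumed.** Also true: over the values shown it runs from 2% to 50% of variance. The direction does not depend on those values.

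**Narrowing to four is harmless.** The four are the protocol's named examples, all scores are still summarised, and fewer ungated tests cannot add false positives. That makes the discrepancy minor, but the statement in Section 6 is still wrong.

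Four stronger readings are tempting, and the documents do not support them:

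- *Selective form loss biases the t-test, so MMRM is required.* Nothing shows that loss is selective. In a simulation with an assumed SD of 25, the t-test was off by 0 to 0.3 points when loss followed the C3D1 score, against a t-test standard error of about 2.0 to 3.1. When loss followed the unseen Week 12 score it was off by 0.4 to 1.0, and MMRM by 0.3 to 1.1, so there was no reliable gain.
- *Unequal progression means unequal form completion.* The 77% and 84% above are a progression proxy. They are not form-completion rates: Protocol 7.5.1 keeps patients on treatment until progression is centrally confirmed.
- *The plan is silent on forms from avapritinib patients who continue after progression.* It is not. SAP 3.2.7 presents efficacy in two groups built on main-period data, and SAP 3.2.2 ends that period at the first dose after continuation or crossover. Those forms are excluded.
- *No form is scheduled at Week 12.* The synopsis does pass from C3D1 to odd cycles: "For all subsequent cycles, all patients will attend study center visits every other cycle on Day 1 of odd cycles (ie, C5D1, C7D1 etc". But Protocol 7.5.3 refers to Table 2 for the form schedule, and Table 2, Protocol 4.1 and the SAP visit window all include C4D1. Only the synopsis is out of line.

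**Conclusion.** The point holds on both parts.

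On method, the planned test is valid if form loss is unrelated to outcome, but it is less precise than the collected data allow. At equal SDs and an assumed correlation of 0.3 to 0.7, baseline adjustment removes 35% to 15% of the variance. The gain could be as small as 2% if scores are more variable at Week 12 and strongly correlated with baseline. MMRM is an acceptable option with a small further gain; the documents give no ground for calling it necessary.

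On scope, the finding needs no assumption. The protocol tests 15 scores, the SAP tests four, and the statement of no change in SAP Section 6 is incorrect on this point.

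This is worth correcting, but it bears only on an additional secondary endpoint. PFS, ORR and OS are unaffected.

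**What to change.** 1. In SAP 4.6.3.6, replace the t-test with an ANCOVA of the Week 12 score on treatment, baseline score and the stratification factors (with the collapsing rules of SAP 3.1), and report the treatment contrast with its 95% CI. An MMRM of the C2D1, C3D1 and C4D1 scores is an alternative if its missing-at-random assumption is stated. A delta-adjusted sensitivity analysis would be optional.
2. In SAP Section 6, declare the change of method. Also declare the restriction to four scores with its reason, or analyse all 15.
3. Either way, label the QLQ-C30 p-values nominal, since they have no multiplicity control.
4. As housekeeping, align the visit list in the protocol synopsis with Protocol 4.1 and Table 2 so that C4D1 appears.

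The cost is SAP wording and standard programming, with no new data. The synopsis line can wait for the next protocol amendment.

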**4.6.3.7 Abdominal Pain**

Abdominal pain is measured as a numeric rating scale (0-10).

For each scheduled assessment a summary will be given of the observed data. In addition, for post-baseline assessments, the change and percentage change from baseline will also be summarized.

**4.6.4 Analysis of Exploratory Efficacy Endpoints**

[Redacted]

[Redacted]

[Redacted]

4.6.4.6 [Redacted]

[Redacted]

[Redacted]

[Redacted]

[Redacted]

#### **4.6.5 Subgroup Analysis**

For ORR, DOR, and PFS as assessed by central radiology, and OS, the following subgroup analyses will be conducted. Corresponding forest plots will be provided based on the odds ratio or hazard ratio by treatment for each subgroup. Analyses will only be performed if the subgroup contains  $\geq 5$  patients.

- Age (<65 years,  $\geq 65$  years)
- Gender (Male, Female)
- Region (US, Europe, Asia, Other) \*Australia to be combined with Europe
- Race (White, Asian, Other)
- Largest target lesion ( $\leq 10$  cm,  $> 10$  cm)
- ECOG Performance Score at Baseline (0, 1)
- V654A or T670I Mutation Status (Present, Absent)
- PDGFRA D842V Mutation Status (Present, Absent)
- Stratification factors (Respective stratification levels).
- The following subgroup analyses will be performed in patients who are V654A mutation negative and T670I mutation negative:
  - D816X Mutation Status (Present, Absent)
  - D820X Mutation Status (Present, Absent)
  - N822X Mutation Status (Present, Absent)
  - Y823X Mutation Status (Present, Absent)

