#### 10.5.3.2.5 Duration of Response

Duration of response (CR or PR) is calculated from the date of initial documentation of a response to the date of first documentation of PD or death due to any cause. Censoring rules for DOR will be similar to those for PFS.

The Kaplan-Meier method will be used to descriptively summarize DOR. No inferential statistics will be performed.

[REDACTED]

[REDACTED]

[REDACTED]

[REDACTED]

[REDACTED]

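### SAP 4.6.5 includes duration of response in the between-arm subgroup forest plots, although the protocol keeps it descriptive and the comparison is confined to responders

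*SAP*

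**What the plan says.** The protocol's analysis section for DOR (10.5.3.2.5) is short: "The Kaplan-Meier method will be used to descriptively summarize DOR", and then "No inferential statistics will be performed".

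The SAP's own DOR section (4.6.3.3) keeps to that. It plans Kaplan-Meier medians, quartiles and landmark estimates, with no test and no hazard ratio. It also fixes the analysis set: "Duration of response will be analyzed for the responders (CR/PR) in the ITT Population using KM methods", and "Patients without CR or PR will be excluded from this analysis".

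SAP 4.6.5 goes further. It opens with "For ORR, DOR, and PFS as assessed by central radiology, and OS, the following subgroup analyses will be conducted" and continues with "Corresponding forest plots will be provided based on the odds ratio or hazard ratio by treatment for each subgroup". The only size condition is "Analyses will only be performed if the subgroup contains" five or more patients. It does not say whether that number applies per arm, to responders or to events.

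SAP 6 then states: "There is no change to planned analyses from the protocol".

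**The concern.** There are two separate problems. The first is a conflict between the documents. A hazard ratio between arms is a comparative model estimate, which goes beyond the descriptive summary in the protocol, and SAP 6 does not declare the addition. The SAP also plans no DOR hazard ratio for the whole population, so the subgroup ratios would stand without an overall estimate beside them.

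The second is what the ratio would mean. Response is itself an outcome of treatment, and the plan expects it to be three times as frequent on avapritinib. The two groups of responders are therefore different selections from their arms, and randomization does not make them comparable. A reader who sees DOR hazard ratios plotted beside those for PFS and OS could take them as evidence that responses last longer or shorter on avapritinib in a given subgroup. The data could not support that reading.

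**Working it through.** **Inputs from the documents.** Arm sizes are about 230 each (protocol 5.1). The assumed ORRs are 5% and 15%, with a stated power of about 95% (protocol 10.2) at two-sided 0.05 (SAP 1.3). Fourth-TKI patients are capped at 30% of enrollment and third-TKI patients are at least 70% (protocol 5.1).

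**Inputs assumed here.** The documents do not say what fraction of responders will have progressed or died by the analysis, so I show 100% (the best case) and 50%. I also assume that the planned ORRs apply within subgroups and that subgroups split evenly between arms.

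**The plan's own figure.** Two-proportion power with pooled variance under the null and n = 230 per arm:

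z = [0.10 × √230 − 1.96 × √(2 × 0.10 × 0.90)] / √(0.05 × 0.95 + 0.15 × 0.85) = (1.517 − 0.832) / 0.418 = 1.64, which gives power 0.949. The stated 95% is reproduced, so the ORR inputs can be used.

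**Expected responders.** Regorafenib: 230 × 0.05 = 11.5 (binomial 95% range 6 to 18). Avapritinib: 230 × 0.15 = 34.5. At the 6/133 response rate the protocol reports for regorafenib in its earlier placebo-controlled trial (section 1.1.2), the regorafenib figure would be 230 × 6/133 = 10.4.

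**Precision of a DOR hazard ratio.** SE(log HR) ≈ √(1/d₁ + 1/d₂), where d₁ and d₂ are the DOR events in each arm. The 95% limits are the estimate divided and multiplied by exp(1.96 × SE).

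- Whole trial, all responders with an event: √(1/11.5 + 1/34.5) = 0.341, factor 1.95.
- Whole trial, half with an event: √(1/5.75 + 1/17.25) = 0.482, factor 2.57.

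| Set | Expected responders (regorafenib / avapritinib) | Factor, 100% events | Factor, 50% events | Chance of no regorafenib responder |
|---|---|---|---|---|
| All patients | 11.5 / 34.5 | 1.95 | 2.57 | negligible |
| 70% (third TKI, minimum) | 8.05 / 24.15 | 2.22 | 3.09 | below 0.1% |
| 50% (illustrative) | 5.75 / 17.25 | 2.57 | 3.80 | 0.95^115 = 0.3% |
| 30% (fourth TKI, at the cap) | 3.45 / 10.35 | 3.38 | 5.60 | 0.95^69 = 3% |
| 10% (illustrative) | 1.15 / 3.45 | 8.25 | 19.8 | 0.95^23 = 31% |

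The normal approximation is rough in the bottom rows. Those figures show the order of imprecision only.

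**The five-patient floor.** The text can be read in two ways for DOR.

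- If it counts patients, a qualifying subgroup of five, averaging 2.5 per arm, expects 2.5 × 0.05 = 0.125 regorafenib responders.
- If it counts responders, each responder comes from the avapritinib arm with probability 15/(15 + 5) = 0.75. All five do so with probability 0.75⁵ = 24%, and no hazard ratio can then be estimated.

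Neither reading ensures responders in both arms.

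**The case against.** The strongest defence is that SAP 4.6.5 specifies no test, p-value or confidence interval for DOR. A hazard ratio shown as a point estimate might pass as descriptive, and the protocol's secondary objective (2.2) does speak of DOR compared with regorafenib. On this view a shared subgroup sentence was simply not tailored to DOR. That may well be how it arose, and it does mean the documents do not support inferring that the SAP plans formal DOR testing. But the protocol's analysis section says how the objective is to be met, namely descriptively, and Kaplan-Meier curves by arm do that. A between-arm hazard ratio is a comparative estimate, forest plots normally carry intervals, and the responder-only problem remains with or without them.

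A reader might also infer that most subgroup rows would contain almost no regorafenib data. The documents do not show this. They give few subgroup sizes, and a half-size subgroup still expects about 5.75 regorafenib responders. Imprecision is established; absence of data in most rows is not. Nor can the floor be taken as certainly counting all patients: because non-responders are excluded from DOR, it may mean responders. In the illustrative subgroup of 23 per arm, where 1.15 + 3.45 = 4.6 responders are expected, that reading would suppress the row about half the time. SAP 7.3 also has a convention for reporting values that cannot be estimated.

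Finally, DOR lies outside the PFS, ORR, OS testing sequence (SAP 4.6.1), so type I error for those endpoints is not at risk. That stands in full and limits the importance of the point.

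**Conclusion.** The point holds as an undeclared inconsistency between protocol and SAP that would produce a potentially misleading display. SAP 4.6.5, read as written, calls for DOR hazard ratios between arms by subgroup. The protocol does not provide for them, and SAP 6 says nothing has changed. The comparison has no randomized basis, whatever its precision.

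Under the plan's own ORRs, the overall 95% limits would span a factor of about 1.95 to 2.6 either way as the event fraction falls from 100% to 50%. Among fourth-TKI patients at the 30% cap, with about 3.5 regorafenib responders, the factor would be about 3.4 to 5.6. These sizes rest on the planned response rates holding, in subgroups as well as overall, and on the assumed event fractions. The textual conflict and the selection problem do not depend on them. No primary or key secondary conclusion is affected.

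**What to change.** Remove DOR from the hazard-ratio forest plots in SAP 4.6.5, leaving ORR, PFS and OS. If subgroup DOR is wanted, present Kaplan-Meier summaries by arm with the number of responders and events in each, labelled descriptive. SAP 6 then needs no entry on this point. Should the sponsor keep the DOR hazard ratios, SAP 6 must declare them as a change from the protocol, and SAP 4.6.5 must state whether the floor of five refers to patients or responders and require responders in both arms.

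The cost is a few words in the SAP and fewer outputs. Sample size, data collection and the PFS, ORR and OS tests do not change. The only loss is an exploratory display.
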